6. ASSESSMENT AND FOLLOW-UP	13
7. STATISTICS AND DATA ANALYSIS	13
8. REGULATORY ISSUES	15
8.1. Ethics approval	15
8.2. Consent	15
8.3. Confidentiality	16
8.4. Indemnity	16
8.5. Sponsor	16
8.6. Funding	16
8.7. Audits	16
9. STUDY MANAGEMENT	16
10. PUBLICATION POLICY	16
11. References	17

Glossary of Abbreviations

Abbreviation	Definition
ECG	Electrocardiogram
AF	Atrial fibrillation
pAF	Paroxysmal atrial fibrillation
PsAF	Persistent atrial fibrillation
ECGI	Electrocardiographic imaging
DCCV	Direct current cardioversion

Keywords

atrial fibrillation, ablation, electrophenotype, ECGI

Study summary

TITLE	Identification of specific electrophenotypes in human atrial fibrillation – INSPECT-AF
DESIGN	Single Centre, Observational Study
AIMS	
1. Investigate the range of AF electrophenotypes and mechanisms in human AF and identify the important functional, structural and clinical determinants of the AF electrophenotype2. Develop the use of non-invasive modalities to classify the underlying AF electrophenotype
OUTCOME MEASURES	
1. Freedom from AF2. AF burden3. Quality of life
POPULATION	Patients with atrial fibrillation due to undergo first time atrial fibrillation ablation or DCCV for under clinical grounds at Hammersmith Hospital
ELIGIBILITY	Adult patients 18-85 years, who are able to give informed consent,
DURATION	4 years

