1. All patients will have up to 252 electrodes placed on their chest and back **2. Surface electrical data will be collected before the procedure and removed prior to the DCCV**

2. All patients will have sedation delivered by an Anaesthetist
3. Up to 3 synchronised shocks will be delivered in accordance with routine clinical practice
4. Patient recovery

AF ablation protocol

The AF ablation procedure will take place in the electrophysiology laboratory. The procedure routinely takes place under general anaesthetic. The procedure typically lasts 2-3 hours.

1. All patients will have up to 252 electrodes placed on their chest and back, with gaps where necessary for patches/electrodes for clinical use

2. Surface electrical data will be collected throughout the procedure from the multiple electrodes

3. A subgroup of patients will have thoracic and cardiac MRI with gadolinium contrast

4. All patients will be out under general anaesthetic by a Consultant Anaesthetist.

5. All patients will have a Transoesophageal echocardiogram to exclude LAA thrombus.

6. All patients have sheaths (small plastic tubes) inserted through their groin veins (femoral veins).

7. A transseptal puncture will be performed to gain access to the left atrium under heparin cover.

8. Cardiac ablation and mapping catheters (small plastic tubes with electrodes at the end) are advanced into the heart under fluoroscopic guidance.

9. A 3D model of the heart will be created to help guide ablation using clinical software (Ensite Precision, Abbott UK or CARTO, Biosense Webster).

10. Electrical mapping data will be collected while the patient is in AF using a dedicated mapping catheter (Lasso or AFocusII/HD grid)

11. Adenosine will be administered through a central venous sheath to induce transient AV block, during which surface electrical data will be collected

12. Pulmonary Vein Isolation ablation with radiofrequency energy will be completed as per standard of care.

13. Electrical mapping data will be collected after pulmonary vein isolation if the patient has remained in AF.

14. All patients will be cardioverted as part of the standard of care.

15. Heparin reversal with Protamine.

16. Sheath removal

17. End of procedure

18. Patient recovery

Steps in bold above will be additional to the standard of care.

After the procedure has finished and all devices have been removed from the patient, we will export each patient's pseudonymised data for further offline analysis

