4.2. Inclusion criteria

Patients with atrial Fibrillation that have been put forward for an ablation or DCCV based on clinical grounds.

- Suitable candidate for catheter mapping/ablation or direct current cardioversion for atrial fibrillation
- Eighteen (18) to eighty-five (85) years of age
- Able to give informed consent

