7. STATISTICS AND DATA ANALYSIS

We will use the data collected to investigate the specific determinants of AF mechanism and electrophenotype. Patients will be classified into a range of AF mechanisms and electrophenotypes, ranging from organised AF sustained by localised drivers through to disorganised AF. The specific functional (e.g. atrial

conduction properties), structural (e.g. left atrial fibrosis burden) and clinical (e.g. AF duration) determinants of the AF electrophenotype will be investigated.

Intracardiac EGM data and 252 lead ECG

The 252 electrode device data will be analysed using a combination of established signal processing (dominant frequency, phase mapping and Shannon entropy) and machine learning techniques (unsupervised learning to cluster data into distinct phenogroups. For the subset of 10 patients with MRI data, we apply our 'in house' inverse solution and Tikhonov regularisation steps to reconstruct the epicardial electrograms.

Cardiac MRI

I will analyse burden of fibrosis and fibrosis distribution patterns and correlate these with the electrogram data.

AF electrophenotype will be determined using the analyses above. I will characterise each patient using both a regional and a global approach. The regional approach will analyse each sequentially collected 'kernel' of data from the RA and LA and assign a metric of organisation. The electrophenotype of a single patient therefore will be described by the number of organised/disorganised sites. The global approach will assign a global metric of organisation, including data from all collected kernels from both RA and LA. I will investigate the determinants of electrophenotype by correlating electrophenotype with clinical parameters including AF duration, co-morbidities and left atrial size on echocardiography. I will also compare intracardiac mapping pre- and post- PVI to investigate the impact of PVI on AF electrophenotype. I will investigate the degree to which the AF electrophenotype can predict outcomes compared to conventional clinical and echocardiographic predictors.

Biomarkers for identification of AF electrophenotype

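### The pre/post-PVI comparison omits patients whose AF stops during PVI and has no rule for them, and the regional metric is a site count without a denominator, so the estimated impact of PVI may be biased

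*Combined protocol and SAP*

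**What the plan says.** **When maps are taken.** The AF ablation protocol in section 3.2 describes the first map at step 10: "Electrical mapping data will be collected while the patient is in AF using a dedicated mapping catheter". PVI is step 12. Step 13 then says "Electrical mapping data will be collected after pulmonary vein isolation if the patient has remained in AF". Cardioversion follows at step 14.

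**What is compared.** Section 7 states: "I will also compare intracardiac mapping pre- and post- PVI to investigate the impact of PVI on AF electrophenotype". It does not say whether the comparison is within patients, who is included, or what happens to a patient with a first map and no second.

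**How electrophenotype is measured.** Section 7 plans two metrics. For the regional one, "The regional approach will analyse each sequentially collected 'kernel' of data from the RA and LA and assign a metric of organisation", and "The electrophenotype of a single patient therefore will be described by the number of organised/disorganised sites". No fixed number of kernels and no denominator is given. For the other, "The global approach will assign a global metric of organisation, including data from all collected kernels from both RA and LA". Its formula is not given and it is not described as a count. The pre/post comparison is not tied to either metric.

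**Who can enter.** The study summary describes the population as "Patients with atrial fibrillation due to undergo first time atrial fibrillation ablation or DCCV". Section 4.2 has "Patients with atrial Fibrillation that have been put forward for an ablation or DCCV based on clinical grounds", and neither 4.2 nor 4.3 restricts entry to a first ablation.

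**The concern.** Whether AF continues after PVI can itself be a result of PVI. The second map therefore exists only for patients selected on something that the treatment may have changed, while the first map carries no such condition. The protocol's own background makes a link between selection and phenotype plausible: it suggests that organised and disorganised AF may call for different ablation approaches. If response to PVI depends on phenotype, leaving AF is unlikely to be random with respect to phenotype.

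The site count adds a second route to a spurious difference. Kernels are collected one after another, so their number may vary between the two maps of one patient and between patients. A shorter second map lowers a raw count even if the AF is unchanged.

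At stake is a statement that PVI organises or disorganises AF when part of the difference comes from who was mapped or how densely. The count wording reaches further than this comparison, because electrophenotype is also to be related to clinical determinants and to outcome. The selection point does not touch freedom from AF, the primary outcome.

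**Working it through.** The plan gives no figure for this comparison, so there is nothing to reproduce.

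**Inputs.** From the documents: a second map only if AF persists; a regional metric defined as a number of sites; 300 patients in total, with the number having ablation not stated. Not in the documents, hence assumed:
- share leaving AF during PVI, 5% to 50%;
- odds ratio for leaving AF of 1, 2 or 3 per SD of pre-PVI organisation, and of 1 or 2 per SD of change;
- pre-PVI organisation X ~ N(0,1), change D ~ N(0, 0.5²), so the true mean effect of PVI is 0.

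**Step 1: two possible analyses.** Leaving AF follows a logistic model in X or in D, with the intercept set to give share t.
- Unpaired: mean of X + D among those still in AF, minus mean of X among all.
- Paired: mean of D among those still in AF.

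Results in SDs of pre-PVI organisation (400,000 simulated patients per scenario):

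| Share leaving AF | Unpaired, OR 2 per SD of X | Paired, same scenario | Paired, OR 2 per SD of D only |
|---|---|---|---|
| 5% | -0.03 | 0.00 | -0.02 |
| 10% | -0.07 | 0.00 | -0.03 |
| 20% | -0.13 | 0.00 | -0.06 |
| 30% | -0.19 | 0.00 | -0.09 |
| 50% | -0.31 | 0.00 | -0.16 |

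With an odds ratio of 3 per SD of X, the unpaired shift runs from -0.05 (5%) to -0.44 (50%). With no link to X or D, both analyses give 0.00.

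Arithmetic check: the overall mean is 0, so t × (mean of leavers) + (1 - t) × (mean of stayers) = 0. At t = 0.20, a stayer mean of -0.13 implies a leaver mean of 0.13 × 0.80 / 0.20 = 0.52 SD, a moderate difference.

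The sign is negative because more organised AF was assumed to stop more often. The opposite assumption reverses it.

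**Step 2: a real effect.** Let the true mean change be +0.5 SD, with an odds ratio of 2 for leaving AF per unit of post-PVI organisation (one pre-PVI SD). The paired estimate is +0.49 at 5% leaving, +0.48 at 10%, +0.47 at 20% and +0.45 at 30%. The attenuation is small under this rule. A sharper rule, or a wider spread of change, makes it larger.

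**Step 3: counts.** Organised count = kernels mapped × share organised. Hold the share at 0.40 and start from 20 kernels (8 organised, 12 disorganised):

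| Kernels in second map | Organised | Disorganised | Change in organised count | Proportion organised |
|---|---|---|---|---|
| 20 | 8 | 12 | 0% | 0.40 |
| 18 | 7.2 | 10.8 | -10% | 0.40 |
| 15 | 6 | 9 | -25% | 0.40 |
| 10 | 4 | 6 | -50% | 0.40 |

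The proportion removes the artefact. The kernel numbers are illustrative.

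**The case against.** A reader might infer that the estimated effect of PVI is necessarily biased. The documents do not support that. The same patient is mapped before and after PVI in one procedure, so a within-patient comparison is the natural reading, and nothing in section 7 says the analysis is unpaired. A paired comparison among patients still in AF is a valid description of that group, and it gives 0.00 wherever leaving AF depends only on baseline. Step 13 is also partly unavoidable, because an AF electrophenotype is not defined outside AF. Paroxysmal AF is excluded in section 4.3, so a large share leaving AF cannot be presumed. The comparison is one exploratory analysis among many.

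A reader might also infer that the regional metric is unusable. That goes too far. If both the organised and the disorganised count are kept, the total and the proportion follow by arithmetic: 6 / (6 + 9) = 0.40. The global metric offers a parallel route.

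Most of this stands, and it limits the point to what may happen. Three things remain. Pairing is not stated. Pairing does not remove selection when leaving AF depends on the change. And describing the result as the impact of PVI, with no account of patients whose AF stopped, extends it beyond the patients it describes. On counts, the plan could derive a proportion but does not say that it will.

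**Conclusion.** The concern holds as a risk, not as a demonstrated bias. As written, patients whose AF stops during PVI drop out of an analysis meant to show what PVI does, and mapping density can enter the regional metric.

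Neither size nor direction can be found from the documents, which give no share leaving AF, no link between leaving AF and organisation, and no kernel number. Over an assumed 5-30% leaving AF with an odds ratio of 2, a null effect shifts by about -0.03 to -0.19 SD if the comparison is unpaired and leaving depends on baseline. If it is paired, the shift is 0.00 in that scenario and about -0.02 to -0.09 SD when leaving depends on the change instead. That last shift is measured against a hypothetical quantity, the change that would have been seen had AF continued in everyone. This is a reason to report leaving AF as a result in its own right rather than try to correct for it.

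The difference between the summary and sections 4.2/4.3 over first-time ablation is a separate eligibility inconsistency. It matters here only because repeat-ablation patients, if enrolled, may have had their veins isolated already.

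**What to change.** - **Rhythm as an outcome.** For every patient mapped in AF before PVI, record rhythm at the end of PVI and before the step 14 cardioversion: still in AF, sinus rhythm, or organised atrial tachycardia/flutter. Report it by baseline electrophenotype. The third category is needed because these patients also have no second AF map.
- **Map-to-map change.** State that it is analysed in within-patient pairs only, label it as conditional on AF persisting, and give the number and baseline electrophenotype of patients without a second map. Name the metric, regional or global, on which it is based.
- **Regional metric.** Define it as the proportion of mapped kernels that are organised, by chamber, with the denominator shown. Use the same definition wherever the regional metric appears.
- **Eligibility, separately.** Reconcile the summary with sections 4.2 and 4.3 on first-time ablation, or analyse any repeat-ablation patients separately in this comparison.

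The cost is SAP wording and a little more analysis. No new procedure is needed: step 13 already requires the team to know whether AF has persisted, so the added item is an explicit record of the rhythm. The price is that the conclusion on map change is limited to patients who remain in AF.

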4. PARTICIPANT ENTRY

4.1. Pre-registration evaluations

All patients enrolled in this study will have the usual standard of care NHS pre-procedural assessment for an ablation or DCCV for Atrial Fibrillation.

4.2. Inclusion criteria

Patients with atrial Fibrillation that have been put forward for an ablation or DCCV based on clinical grounds.

- Suitable candidate for catheter mapping/ablation or direct current cardioversion for atrial fibrillation
- Eighteen (18) to eighty-five (85) years of age
- Able to give informed consent

4.3. Exclusion criteria

- Severe cerebrovascular disease
- Moderate to severe renal impairment (eGFR < 30)
- Active gastrointestinal bleeding
- Active infection or fever
- Short life expectancy
- Significant anaemia
- Severe uncontrolled systemic hypertension
- Severe electrolyte imbalance
- Congestive heart failure - NYHA Class IV
- Recent myocardial infarction
- Bleeding or clotting disorders
- Paroxysmal Atrial Fibrillation
- Uncontrolled diabetes
- Inability to receive IV or oral Anticoagulants
- Unable to give informed consent (these patients would not be recruited)

- Pregnancy

4.4. Withdrawal criteria

- One of the exclusion criteria are fulfilled during the study period
- Patient wishes to withdraw from study

If criteria are fulfilled for exclusion during the study period patient will be withdrawn by investigators.

If patient wishes to withdraw, they can inform any staff involved in the study in writing or in person or any other mode of communication, and they will be withdrawn.

In all cases of withdrawal data will be kept and used in the study up to the time of withdrawal.

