3.1. Study outcome measures

We will classify patients into electrophenotypes based on the invasive and non-invasive data collected. The primary outcome measure will be freedom from AF. Secondary outcome measures will be AF burden and quality of life.

[figure not shown]

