6. ASSESSMENT AND FOLLOW-UP

Patients undergoing AF ablation and the 252 lead ECG protocol will be provided with an AliveCor device to use up to once per day and when they have symptoms to accurately monitor for recurrence of AF. They will also be asked to complete symptom score (36-Item Short Form Survey Instrument (SF-36) and Atrial Fibrillation Effect on Quality-of-life (AFEQT)) questionnaires up to once per month. They will have Holter monitoring and clinical follow up in line with routine clinical care.

Patients undergoing DCCV will be followed as per routine clinical care for 1 year.

The end of study is when the last patient has completed their last follow up visit.

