8.2. Consent

Consent to enter the study must be sought from each participant only after a full explanation has been given, an information leaflet offered, and time allowed for consideration. Signed participant consent should be obtained. We will gain consent for participation in the study at Hammersmith Hospital. Consent for participation in the study can be gained by a consultant or registrar who is familiar with the study, clinical research fellow, or study nurse. Consent for the ablation procedure will be gained on the day of the procedure by the consultant performing the ablation or a specialty registrar who is familiar with the procedure, following normal clinical practice.

The right of the participant to refuse to participate without giving reasons must be respected. After the participant has entered the study the clinician remains free to

give alternative treatment to that specified in the protocol at any stage if he/she feels it is in the participant's best interest, but the reasons for doing so should be recorded. In these cases, the participants remain within the study for the purposes of follow-up and data analysis. All participants are free to withdraw at any time from the protocol treatment without giving reasons and without prejudicing further treatment.

In case of loss of capacity during the study period, the participant will be withdrawn from the study. Identifiable data or tissue already collected with consent would be retained and used in the study. No further data or tissue will be collected, or any other research procedures carried out on or in relation to the participant. We will ensure informed consent is gained for use of collected data in case of incapacity, at a time when the patient has the capacity to make this decision.

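### Section 4.4 ends follow-up when an exclusion criterion arises later, including paroxysmal AF, so AF burden and quality of life are lost for outcome-related reasons

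*Combined protocol and SAP*

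**What the plan says.** Section 4.4 gives two grounds for withdrawal. One is the patient's wish. The other is "One of the exclusion criteria are fulfilled during the study period". The section then makes the second ground mandatory: "If criteria are fulfilled for exclusion during the study period patient will be withdrawn by investigators". No criterion is exempted.

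The section 4.3 list includes "Paroxysmal Atrial Fibrillation", with nothing to limit it to the type of AF at entry. It also names conditions that can appear at any time, such as infection or fever, gastrointestinal bleeding, significant anaemia, recent myocardial infarction and NYHA class IV heart failure.

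On data handling, section 4.4 adds: "In all cases of withdrawal data will be kept and used in the study up to the time of withdrawal".

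The outcomes are in section 3.1: "The primary outcome measure will be freedom from AF" and "Secondary outcome measures will be AF burden and quality of life". Under section 6, patients in the ablation and 252-lead protocol receive a handheld ECG device to "use up to once per day and when they have symptoms to accurately monitor for recurrence of AF", with questionnaires up to monthly. Section 6 also places the end of the study at the last patient's final follow-up visit. Section 7 relates all three outcomes to electrophenotype group, to see which groups gain most from ablation.

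**The concern.** The entry exclusions are reused as withdrawal rules for the whole study, and one of them overlaps with the outcome. The patients enrolled have non-paroxysmal AF. If the arrhythmia returns after ablation in a paroxysmal pattern, the patient now fits an exclusion criterion and, on the text, must be withdrawn. The same holds for a patient who develops an infection, a bleed or an infarction, or whose heart failure worsens to class IV.

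Loss of follow-up is then linked to how the patient is doing. AF burden and quality of life suffer most, because both need observation after a first recurrence. If the pattern of recurrence differs between electrophenotypes (plausible, but not stated in the documents), the loss differs between the groups that section 7 sets out to compare.

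**Working it through.** The plan gives no figure to reproduce on this point. It states no dropout allowance, no expected recurrence rate for its own patients and no rule for how withdrawals are analysed. The check is therefore a reading of the sections, followed by an illustration.

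**Reading**

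1. Trigger: any 4.3 criterion met in the study period (4.4). Section 6 runs the study to the last follow-up visit, so follow-up is included.
2. Which recurrences trigger it: only those fitting the paroxysmal criterion. Persistent AF is not on the 4.3 list.
3. What is kept: everything up to withdrawal (4.4). The recurrence that prompts withdrawal is already recorded.
4. What is lost: everything later, meaning device recordings, Holter results used by the study, and questionnaires.
5. Whether the recorded recurrence counts as an event: not stated. Sections 3.1 and 7 give no time point, blanking period or censoring rule for freedom from AF.

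**Illustration for ablation patients**

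Inputs:
- True freedom from AF, f = 0.50. This is the background success rate for persistent AF in section 1.1, not a design assumption.
- Share of recurrences that are paroxysmal, s = 0.2, 0.4 or 0.6. This is an assumption; the documents give no value.

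Formulas:
- Triggering recurrence counted as an event: f
- Withdrawn patients dropped (completers only): f / (1 − (1 − f)s)
- Withdrawn patients censored (Kaplan-Meier): f^(1 − s), assuming proportional hazards for paroxysmal and persistent recurrence and independence between them
- Withdrawn patients treated as event-free: f + (1 − f)s
- Share of ablated patients losing later follow-up: (1 − f)s

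| | s = 0.2 | s = 0.4 | s = 0.6 |
|---|---|---|---|
| Counted as event | 50% | 50% | 50% |
| Dropped | 0.5/0.9 = 56% | 0.5/0.8 = 63% | 0.5/0.7 = 71% |
| Censored | 0.5^0.8 = 57% | 0.5^0.6 = 66% | 0.5^0.4 = 76% |
| Treated as event-free | 0.5 + 0.1 = 60% | 0.5 + 0.2 = 70% | 0.5 + 0.3 = 80% |
| Lose later burden and QoL data | 10% | 20% | 30% |

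The first row shows no bias at any s. The next three show what happens if the analysis does not count the triggering recurrence. The last row applies whichever analysis of freedom from AF is chosen.

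For AF burden, the direction of bias cannot be fixed. If burden is computed from the retained data, a withdrawn patient contributes mainly the time before recurrence, and burden is understated for that patient. If withdrawn patients are dropped, the result depends on the mix of AF-free and persistently recurrent patients who remain.

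**The case against.** The strongest reply is that the paroxysmal criterion was meant to describe AF type at entry, and that no investigator would withdraw a patient for having the study's outcome. That may be the intention. However, 4.4 applies the whole list during the study and makes withdrawal mandatory, so the text has to be changed to say so. The documents also do not define paroxysmal AF or say how a recurrence would be classified. Section 3.2 ties the end of participation to recruitment of 300 patients, whereas section 6 ties the end of the study to follow-up. Both points leave the trigger uncertain; neither removes it.

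A second reply is that the primary objective in section 2 concerns electrophenotypes and their determinants, which rest largely on data taken at or before the procedure. This stands. Those data survive later withdrawal, and the damage is confined to the outcome analyses.

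Several stronger readings are tempting and should be resisted.

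- A reader might infer that patients who have the primary outcome are removed from it. Persistent recurrence triggers no withdrawal, and the data-retention sentence keeps the paroxysmal recurrence on record.
- A reader might infer that section 8.2 contradicts 4.4, because it says "the participants remain within the study for the purposes of follow-up and data analysis". That sentence covers patients given alternative treatment, a different situation, and the same section stops data collection on loss of capacity. It shows that the protocol can separate treatment from follow-up, no more.
- A reader might infer that complications go unrecorded. The event that prompts withdrawal is in the retained data, and section 5.2 requires adverse events to be reported. Only what happens afterwards is at risk.

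**Conclusion.** The concern holds for AF burden and quality of life. Following 4.4 as written ends observation because of an outcome-related event, and the loss is selective. Under the assumptions above it would affect 10-30% of ablated patients through the paroxysmal trigger alone; the other post-procedure conditions add an amount that the documents do not allow one to estimate.

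For freedom from AF the conclusion is conditional. With regard to the paroxysmal trigger, the bias is zero if the triggering recurrence counts as an event. If those patients are dropped, censored or treated as event-free, a true 50% reads 56-71%, 57-76% or 60-80% respectively. The documents specify none of these analyses, so a flat statement that freedom from AF is overstated is not supported.

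The percentages rest on an assumed paroxysmal share and on a background success rate. Section 1.1 says that many recurrences after ablation are flutter or atrial tachycardia rather than AF, so the share of patients with AF recurrence may be below 50% and the effect smaller. The 50% figure says nothing about the DCCV patients.

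**What to change.** In section 4.4, separate stopping research procedures from stopping follow-up. State that a patient who meets a 4.3 criterion after enrolment, paroxysmal recurrence included, stays in rhythm, quality-of-life and safety follow-up and in the analysis, unless consent is withdrawn or capacity is lost (section 8.2). Record the date and reason for every withdrawal.

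In sections 3.1 and 7, state that AF recurrence of any pattern counts as an event for freedom from AF, and say how withdrawals enter each of the three outcomes.

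Do not solve this simply by confining 4.3 to enrolment. Patients are recruited before research procedures that include gadolinium MRI and adenosine, and the list contains items such as renal impairment and pregnancy. The sponsor should reconcile 4.3 and 4.4 on which criteria stop any remaining research procedures; no clinical rule is proposed here.

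The cost is a short amendment. No extra visits are needed, because these patients remain under routine care. The small downside is slightly more follow-up data to collect.
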